**REGULATORY FRAMEWORK:**

Please indicate all that apply:

	DOD (Department of Defense)
	DOE (Department of Energy)
	DOJ (Department of Justice)
	ED (Department of Education)
	EPA (Environmental Protection Agency)
	FDA (Food and Drug Administration)
	HHS (Department of Health and Human Services)
	VA
	Other:

Is this a clinical trial under ICH-GCP E6?  Yes  No

If yes, please confirm that the research team is familiar with and agrees to comply with the investigator requirements cited in ICH-GCP E6.  Yes  No

ICH-GCP E6 can be accessed by copying and pasting this URL into your browser: <http://www.fda.gov/downloads/Drugs/Guidances/ucm073122.pdf>

PROTOCOL TITLE: Transcranial direct current stimulation for treatment of deficits after traumatic brain injury.

PROTOCOL TITLE: Transcranial direct current stimulation for treatment of deficits after traumatic brain injury.

## 1. Objectives

Our long-term goal is to develop safe and effective treatments for symptoms of mild to moderate TBI (mmTBI) that restore patients to higher levels of functioning, decrease disability, and promote brain healing. The objective of this application is to investigate the use of transcranial direct current stimulation (tDCS) to treat symptoms of executive dysfunction and depression in patients with mmTBI. Our central hypotheses are (1) tDCS paired with relevant cognitive training facilitates improves executive function on NIH-approved neuropsychological measures, (2) tDCS reduces depression scores on NIH Common Data Elements for TBI, (3) that these improvements in emotion and cognition will be detectable up to one year after stimulation, (4) (4) certain clinical variables will reliably predict response to tDCS, such as age, education level, injury severity, and magnetic resonance imaging (MRI) evidence of structural/functional/metabolic abnormalities and (5) quantitative electroencephalography (EEG) will demonstrate changes in frontal midline theta band power and theta band synchrony, markers of cognitive control, in responders. These objectives were formulated based on our clinical experience with [name] (project mentor) characterizing symptomatic patients with mmTBI in the post-acute setting, groundbreaking research led by [name] (project mentor) that has demonstrated robust increases in attention and learning with tDCS, and extensive evidence accumulated by co-junior investigator on the grant application [name] on EEG measures of executive dysfunction.

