### Specific Aim 1: tDCS for executive dysfunction in mmTBI

Experiments in this aim will test the hypothesis that in patients with mmTBI, left prefrontal anodal tDCS concurrent with cognitive training for up to ten consecutive weekdays will result in significantly more improvement in executive function compared to sham stimulation. Patients with cognitive complaints 3 months to 15 years after mmTBI will be recruited from local emergency departments and brain injury clinics. Healthy controls will also be recruited through flyers, advertisements and word of mouth. Aim 1.1: tDCS will be paired with computer-based cognitive training tasks of response inhibition, set shifting, and working memory, while executive function will be measured with the NIH Examiner battery before, immediately after, and one month after stimulation. Pre-and post-stimulation EEG and MRI may be obtained. During EEG and MRI participants may be asked to rest quietly or perform simple tasks. Aim 1.2: Persistence of post-traumatic symptom reduction and quality of life improvement will be assessed with Common Data Elements instruments via telephone interview at 6 months and one year. Aim 1.3: Clinical predictors of tDCS response including EEG frontal theta synchrony, injury severity, presence of neuroimaging abnormalities, premorbid intelligence, and post-traumatic symptom burden will be determined with linear mixed-models analysis.

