The current proposal represents a major step towards a solution for post-TBI symptoms that harnesses the intact brain’s neuroplastic potential to overcome a variety of deficits. Transcranial direct current stimulation (tDCS) is a non-invasive form of brain stimulation utilizing low amounts of current to modulate neuronal activity and improve neuropsychiatric symptoms across diverse disorders, including post-stroke aphasia and motor learning, working memory in dementia, and major depression. We will attempt to demonstrate that tDCS produces similar gains in cognitive symptoms among mmTBI patients as we have seen in our lab, as well as improvements in depressive symptoms others have found in depressed patients. We will then correlate response to tDCS with EEG measures of cognitive control and brain connectivity so as to better identify patients likely to benefit from tDCS, as well as clarify the mechanism of therapeutic action of tDCS. Due to its low cost, minimal side effects, and the ease with which it can be integrated with existing rehabilitation approaches, empirical support for tDCS would be a “game-changer” in the field of TBI. Successful completion of our specific aims will have a major impact on research and clinical practice regarding the management of debilitating TBI symptoms. Toxic effects of medications could be avoided; visits to rehabilitation facilities could be reduced; and treatment could be provided in diverse settings. Future studies would elucidate optimal electrode placements and stimulation parameters for specific cognitive symptoms and in specific types of brain injury, as well as provide a rational mechanism of therapeutic action in terms of improved functional brain connectivity. Integration with emerging multimodal neuroimaging techniques may reveal exactly which type of patient benefits from which type of tDCS, personalizing clinical interventions.

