## 5. Study Endpoints

Primary endpoint: change in scores on the EXAMINER battery from before to after stimulation.

Secondary endpoints: change in score on the Neurobehavioral Symptom Inventory, Beck Depression Inventory-II, Hamilton Rating Scale for Depression, change in frontal midline theta synchrony on EEG, change in MRI abnormalities, and quality of life measure from time 0 to 1 year.

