### Experimental Design and Methods

**Participants:** Eighty TBI subjects will be recruited for this study, all having suffered mild or moderate TBI (mmTBI, as defined before) at least 3 months prior to study enrollment, but not more than 15 years prior to enrollment. 80 age- and sex-matched healthy controls will be recruited. All participants will be 18-55 years of age. We will expect to screen approximately 120 patients with mmTBI in order to reach our goal of 80 TBI subjects. The experimental pre-post, double-blind design is graphically displayed. It includes randomization of TBI patients to either a left-sided active transcranial direct current stimulation (tDCS) protocol, or sham treatment group to foster isolation and identification of any tDCS treatment effects. To enhance our statistical power to identify predictors of treatment response in mmTBI patients, 40 TBI subjects and 40 controls will be assigned to each group: left-sham and left-active.

**Recruitment:** Recruitment primarily will be through the UNM Hospital Emergency Department (ED) (the only Level 1 trauma center in New Mexico). The UNM Health Sciences Center (HSC) Clinical and Translational Science Center (CTSC) Participant Recruitment Service (PRS) for Clinical Research will monitor ED intake records for patients who meet criteria once released from the hospital, then notify the study team of these cases. A second means of recruitment will involve direct referrals from UNM and non-UNM ED physicians and/or referrals from any clinic in the Albuquerque metropolitan area, via the distribution of flyers and calls to clinical directors to publicize the study. A third means of recruitment will involve information listed on the UNM CBRR and MRN websites, and posted flyers.

**PROTOCOL TITLE:** Transcranial direct current stimulation for treatment of deficits after traumatic brain injury.

[figure not shown]

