Statistical analyses will utilize the CTSC Biostatistics core. Power analyses and statistical analysis strategy were determined with our statistician [name], who will continue to provide recommendations and support throughout the project. Sufficient group sizes were determined on the basis of data derived from preliminary studies. Clark and colleagues found an effect size of Cohen's  $d = 1.2$  for tDCS to induce improvements in cognition. For our power calculations we will assume a more conservative effect size of  $d = 0.7$  which is consistent with a recent meta-analysis of tDCS effect sizes. With 40 tDCS treatment patients compared to 40 sham patients and an effect size of 0.7, we have 80% power to detect effects of active versus sham treatment in a two-sample t-test. Power in the linear mixed model analysis should be superior that that of the t-test. For Aim 1.1, the central analyses evaluate group (active vs. sham) differences in the EEG data and on the three Examiner composite variables across the three initial time points (before, immediately after, and 1 month after tDCS stimulation protocol). To test this hypothesis, three separate linear mixed models analyses will be performed using the three Examiner composite scores (Fluency, Cognitive Control, Working Memory) as dependent variables. In each analysis, we will incorporate three covariates that may predict variation in learning (severity: mild vs. moderate, premorbid intelligence: WTAR score, and symptom burden: NSI). This will allow us to determine predictors of treatment response (Specific Aim 1.3). Sex, ethnicity, and age will also be entered into the statistical model. The effects of these covariates will be estimated by constructing appropriate contrasts in model effects. A similar set of analyses will evaluate group differences on the variables assessed in our long-term oral/phone follow-up (five data points: (1) before tDCS, (2) immediately after tDCS, (3) 1 month post-tDCS, (4) 6 months, and (5) 1 year) for Aim 1.2. For these analyses dependent variables will be the total cognitive items score of the NSI and the PROMIS-29 profile total score). Significant effects will be followed up with more fine-grained analysis of the components of composite scores. The use of linear mixed-models minimizes the adverse impact of a missing data point, which may well occur in a longitudinal clinical study such as this. Expected attrition will be taken into account with an intention-to-treat analysis. Missing data patterns will be analyzed to assess the extent to which they are informative (in contrast to missing at random), and analyses adjusted accordingly. All EEG data will undergo standard preprocessing (e.g. motion correction, spatial normalization) and quality control prior to statistical modeling. Depending on the specific question of the study, data may be analyzed using the general linear model, independent components analysis, machine learning techniques, or a variety of other standard approaches for neuroimaging data.

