We will also provide all participants and their families with a referral list of community support, treatment, and educational resources about TBI. This information will also be explained during the consent process. In addition, if a participant's status with respect to any of the study criteria change during the experiment (i.e., initiation of substance abuse), the participant's participation in the study may be terminated without their consent. Our consent form will include a statement regarding anticipated circumstances under which the subject's participation may be terminated by the investigator without regard to the subject's consent and a statement indicating that significant new findings developed during the course of the research which may relate to the subject's willingness to continue participation will be provided.

Statistical analyses will utilize the CTSC Biostatistics core. Power analyses and statistical analysis strategy were determined with our statistician [name], who will continue to provide recommendations and support throughout the project. For Aim 1.1, the central analyses evaluate group (active vs. sham) differences on the three Examiner composite variables across the three initial time points (before, immediately after, and 1 month after tDCS stimulation protocol). To test this hypothesis, three separate linear mixed models analyses will be performed using the three Examiner composite scores (Fluency, Cognitive Control, Working Memory) as dependent variables. In each analysis, we will incorporate three covariates that may predict variation in learning (severity: mild vs. moderate, premorbid intelligence: WTAR score, and symptom burden: NSI). This will allow us to determine predictors of treatment response (Specific Aim 1.3). Sex, ethnicity, and age will also be entered into the statistical model. The effects of these covariates will be estimated by constructing appropriate contrasts in model effects. A similar set of analyses will evaluate group differences on the variables assessed in our long-term oral/phone follow-up (five data points: (1) before tDCS, (2)

**PROTOCOL TITLE:** Transcranial direct current stimulation for treatment of deficits after traumatic brain injury.

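### Central hypothesis 5 looks for EEG change in an undefined group picked by outcome, with no sham reference, so it can be confirmed when tDCS does nothing and the planned randomised EEG comparison does not test it

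*Combined protocol and SAP*

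**What the plan says.** Section 1, Objectives, lists five central hypotheses. The fifth is that "quantitative electroencephalography (EEG) will demonstrate changes in frontal midline theta band power and theta band synchrony, markers of cognitive control, in responders". The word responders occurs only there. No score, outcome domain (executive function or depression), cut-off, visit or arm is attached to it.

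Section 2, Background, states the intended link: "We will then correlate response to tDCS with EEG measures of cognitive control and brain connectivity". The rest of that sentence gives two purposes: finding patients likely to benefit, and clarifying how tDCS acts. It names no model and no sham reference.

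The other EEG statements ask different questions:

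- Section 11, Data Analysis: "For Aim 1.1, the central analyses evaluate group (active vs. sham) differences in the EEG data and on the three Examiner composite variables". This compares the randomised arms and does not condition on response.
- Section 14, Data Management/Confidentiality, repeats the analysis plan without EEG: "the central analyses evaluate group (active vs. sham) differences on the three Examiner composite variables across the three initial time points".
- Section 5, Study Endpoints, has a secondary endpoint of "change in frontal midline theta synchrony on EEG". It covers synchrony but not theta power, and it is not restricted to responders.
- Specific Aim 1 (Aim 1.3) refers to "Clinical predictors of tDCS response including EEG frontal theta synchrony", and Aim 2.3 is similar. Here EEG is a predictor of response.

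Section 10, under the cognitive control tasks, provides for the same 30-minute training with active and with sham stimulation.

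**The concern.** Response is an outcome. A rise in EXAMINER score after ten sessions may come from stimulation, from the training given in both arms, from practice on a battery taken three times, or from measurement error. Calling someone a responder to tDCS assumes that stimulation caused the rise. The protocol itself treats frontal theta as a marker of cognitive control, so theta change and executive-score change may well move together in anyone, stimulated or not. Choosing people because their scores rose then also chooses people whose theta moved.

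What is at stake is the mechanism claim. Theta change among improved active-arm patients could be reported as confirming a central hypothesis and as showing how tDCS works, while the randomised comparison shows no effect of stimulation on EEG. Because responders are undefined, the definition could also be settled after the data are seen.

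**Working it through.** **No stated figure to reproduce.** The documents give no sample size, power or alpha for hypothesis 5. The 80% power in section 11 concerns active versus sham patients in a two-sample t-test and does not bear on this point.

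**Which planned analysis tests hypothesis 5 as worded?**

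| Place | Quantity | Conditions on response? | Sham reference? |
|---|---|---|---|
| Section 1, hypothesis 5 | theta power and synchrony change | yes | none stated |
| Section 2, Background | correlation of response with EEG | uses response as a variable | none stated |
| Section 5 | change in theta synchrony | no | not stated |
| Section 11 | EEG, active versus sham | no | yes |
| Section 14 | EXAMINER only | no | yes (no EEG) |
| Aims 1.3 and 2.3 | EEG as predictor of response | no | not stated for EEG |

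None does. The section 11 comparison can be null while hypothesis 5 is declared met, or positive while saying nothing about responders. The covariates named in section 11 (severity, WTAR, NSI, sex, ethnicity, age) do not include EEG, so the Background correlation has no model there either.

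**Illustration with zero tDCS effect.**

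Input from the documents: 40 active TBI patients, from "40 TBI subjects and 40 controls will be assigned to each group: left-sham and left-active" in section 10.

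Assumptions not in the documents:
- EEG change and EXAMINER change are bivariate normal, SD 1, with correlation r in both arms.
- Responders are the better half on EXAMINER change (20 of 40).
- The test is a one-sample t-test of EEG change in responders, two-sided 0.05.
- All 40 have EEG. Section 10 says only that a subset may have it.

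The mean of the upper half of a standard normal is √(2/π) = 0.798. So among responders:

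- mean EEG change = 0.798 r
- SD = √(1 − 0.637 r²)
- noncentrality = 0.798 r × √20 / √(1 − 0.637 r²)

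At r = 0.3: 0.239 × 4.472 / 0.971 = 1.10. At r = 0.5: 0.399 × 4.472 / 0.917 = 1.95. The noncentral t on 19 degrees of freedom then gives the formula column; simulation used 40,000 trials per setting.

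| r | Formula | Simulated, active responders | Simulated, sham responders | Active vs sham, all |
|---|---|---|---|---|
| 0 | 5.0% | 4.8% | 5.2% | 5.0% |
| 0.1 | 6.3% | 6.3% | 6.3% | 5.2% |
| 0.2 | 10.6% | 10.4% | 10.4% | 5.0% |
| 0.3 | 18.2% | 18.1% | 17.6% | 4.8% |
| 0.5 | 45.5% | 44.3% | 44.1% | 4.9% |

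Sham responders show the same rates, so the finding does not point to stimulation.

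**Sensitivity.**
- Training or practice shifts both measures by 0.3 SD in both arms: 25% (r = 0), 50% (0.2), 64% (0.3), 88% (0.5).
- Responders defined as a gain of at least 0.5 SD, no shared gain: 4.9%, 11.6%, 20.4%, 52.0% at the same r values. With the 0.3 SD shared gain: 21.0%, 47.5%, 62.2%, 88.1%.
- Only 15 active patients with EEG, better 7 as responders, no shared gain: 5%, 7%, 9%, 17%.
- Active versus sham in all patients stays at about 5% in every setting.

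**The case against.** The strongest reply is that no such analysis is planned. Sections 11 and 14 contain no responder rule, no responder split and no test within responders, and section 11 already calls the randomised EEG comparison central. This stands, and it limits the point. A reader might infer that the trial's EEG analysis is built on a responder subgroup. The documents do not support that; the fault lies in how hypothesis 5 is worded and in its missing link to the analysis.

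Second, a reader might infer that the patient-selection and predictor aims fail for the same reason. They do not. The patient-selection half of the Background sentence fits Aims 1.3 and 2.3, where theta synchrony is most naturally a pre-stimulation measure. Using a baseline predictor does not select people by outcome. Only the mechanism half is exposed, and it does not say whether baseline EEG or EEG change is meant.

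Third, the correlation, the responder rule and the EEG sample size are assumptions. This also stands. With no correlation and no shared gain the rate is the nominal 5%, so the right word is can.

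Finally, one might compare responders with non-responders and call the rejection rate a false-positive rate. It would not be: the assumed correlation is a real association, and such a test would detect it correctly. The rates above have a narrower meaning: how often hypothesis 5 would be declared confirmed although tDCS does nothing.

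**Conclusion.** The point holds in a confined form. Hypothesis 5 is called central, but it is stated for an undefined group identified by outcome after randomisation, without a sham reference. Read literally, it can be met with no tDCS effect, and the valid active-versus-sham EEG comparison in section 11 does not test it. With 40 active patients, zero tDCS effect and no shared gain, the chance of apparent confirmation runs from about 5% at r = 0 to about 45% at r = 0.5. It is higher if training moves both measures in both arms, and lower with fewer EEG recordings. These sizes rest on assumed correlations and an assumed responder rule; the logical gap does not.

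A reader might infer that the primary analysis is compromised. The documents do not support that: the EXAMINER comparison, the randomised EEG comparison and the baseline-predictor aims are unaffected. What changes is what the trial may conclude about mechanism, so the wording should be corrected.

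**What to change.** 1. Restate hypothesis 5 in section 1 as a greater change in frontal midline theta power and synchrony with active tDCS than with sham, in all randomised TBI participants with EEG.
2. Reconcile the other places with section 11: section 14 omits EEG from the arm comparison, and section 5 lists synchrony but not power.
3. In section 2, label the association between EEG change and EXAMINER change exploratory. Estimate it in both arms in one model, with no responder split: EXAMINER change on arm, EEG change and arm × EEG change, adjusted for baseline EXAMINER and baseline EEG. The sham arm is the reference.
4. State that this model is associational. EEG change is itself measured after randomisation, so even the interaction term does not establish mechanism.

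The cost is some rewording, one extra exploratory model and a weaker mechanism claim. No new data, visits or participants are needed.

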### Specific Aim 1: tDCS for executive dysfunction in mmTBI

Experiments in this aim will test the hypothesis that in patients with mmTBI, left prefrontal anodal tDCS concurrent with cognitive training for up to ten consecutive weekdays will result in significantly more improvement in executive function compared to sham stimulation. Patients with cognitive complaints 3 months to 15 years after mmTBI will be recruited from local emergency departments and brain injury clinics. Healthy controls will also be recruited through flyers, advertisements and word of mouth. Aim 1.1: tDCS will be paired with computer-based cognitive training tasks of response inhibition, set shifting, and working memory, while executive function will be measured with the NIH Examiner battery before, immediately after, and one month after stimulation. Pre-and post-stimulation EEG and MRI may be obtained. During EEG and MRI participants may be asked to rest quietly or perform simple tasks. Aim 1.2: Persistence of post-traumatic symptom reduction and quality of life improvement will be assessed with Common Data Elements instruments via telephone interview at 6 months and one year. Aim 1.3: Clinical predictors of tDCS response including EEG frontal theta synchrony, injury severity, presence of neuroimaging abnormalities, premorbid intelligence, and post-traumatic symptom burden will be determined with linear mixed-models analysis.

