### Specific Aim 2: tDCS for depressive symptoms in mmTBI

Experiments in this aim will test the hypothesis that left prefrontal anodal tDCS in patients with mmTBI will significantly reduce depressive symptoms compared to sham stimulation. Aim 2.1: Patients will be assessed for symptoms of depression via self-report instruments and clinician-administered scales from NIH Common Data Elements before, immediately after, and one month after the stimulation protocol. Aim 2.2: Persistence of antidepressant benefit will be assessed via telephone interview at 6 months and one year. Aim 2.3: clinical predictors of tDCS response such as EEG frontal theta synchrony, injury severity, premorbid intelligence, neuroimaging abnormalities, and symptom burden will be determined.

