#### Experimental Design and Methods

*Participants:* TBI subjects from Aim 1.1 will be carried forward for study in Aim 1.3. Key clinical variables in the study group will be analyzed for association with tDCS effect, namely, lesser post-traumatic symptom burden as measured by the NSI, mild versus moderate severity of TBI, lack of neuroimaging abnormalities on MRI, and higher premorbid level of intelligence as measured by the WTAR, as these are factors shown to predict better recovery from TBI.

Specific Aim 2.1: Effectiveness of tDCS for depression after mmTBI

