### Specific Aim 2.2:

The subjects from Aim 2.1 will be automatically included. At 6 months and 1 year after stimulation, subjects will be contacted via telephone and administered the depression assessment tools utilized before, immediately after, and 1 month after stimulation.

**Specific Aim 2.3:** Subjects from Aim 2.1 will be carried forward for study in Aim 2.3. Patient and injury characteristics will predict positive response to tDCS, namely, higher premorbid intellectual function (WTAR), lesser severity of injury (mild versus moderate), lack of neuroimaging abnormalities on MRI, and more severe pre-stimulation depressive symptoms (BDI, HAM-D). Understanding which of the clinical variables described above moderate the efficacy of tDCS in mmTBI will allow for more precise patient selection and better overall efficacy in future applications.

Each of the 80 participants will receive \$20/hr in the form of cash cards for taking part in the study.. This is felt to be a fair amount that is not coercive and will help decrease attrition for this study which involves many visits.

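### Two of the five Aim 1.3 predictors of tDCS response, EEG frontal theta synchrony and neuroimaging abnormality, have no term in any written model, and no arm-by-predictor interaction is written for any predictor

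*Combined protocol and SAP*

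**What the plan says.** **The aims.** Section 1, Specific Aim 1 (Aim 1.3), sets out to study "Clinical predictors of tDCS response including EEG frontal theta synchrony, injury severity, presence of neuroimaging abnormalities, premorbid intelligence, and post-traumatic symptom burden" using linear mixed models. Specific Aim 2 states that "clinical predictors of tDCS response such as EEG frontal theta synchrony, injury severity, premorbid intelligence, neuroimaging abnormalities, and symptom burden will be determined" (Aim 2.3).

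**The procedures.** Section 10, under Aim 1.3, gives a closed list: "namely, lesser post-traumatic symptom burden as measured by the NSI, mild versus moderate severity of TBI, lack of neuroimaging abnormalities on MRI", and WTAR. Under Aim 2.3 it says "Patient and injury characteristics will predict positive response to tDCS, namely, higher premorbid intellectual function (WTAR", followed by lesser severity, no MRI abnormality and worse baseline BDI and HAM-D scores. It adds that the purpose is to learn which variables moderate the efficacy of tDCS.

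**The models.** Section 11 enters "three covariates that may predict variation in learning (severity: mild vs. moderate, premorbid intelligence: WTAR score, and symptom burden: NSI", adds sex, ethnicity and age, and says that this determines the predictors for Aim 1.3. Covariate effects are to come from contrasts that are not specified. Section 14 repeats this text.

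**Other roles given to EEG.** In section 1, hypothesis 4 says that "certain clinical variables will reliably predict response to tDCS, such as age, education level, injury severity, and magnetic resonance imaging (MRI) evidence" and does not mention EEG as a predictor. Hypothesis 5 says that EEG "will demonstrate changes in frontal midline theta band power and theta band synchrony, markers of cognitive control, in responders". Section 5 lists change in theta synchrony as a secondary endpoint, and section 11 compares EEG data between arms. Section 2 says the team will "correlate response to tDCS with EEG measures of cognitive control and brain connectivity so as to better identify patients likely to benefit from tDCS".

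**Availability.** Specific Aim 1 and section 10 make EEG optional, and section 10 limits it to a subset of unstated size. Section 18 and the section 20 table list EEG without that limit.

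**The concern.** A predictor of response to tDCS, as opposed to sham, is a modifier of the treatment effect. The plan's stated purpose of moderation needs a term that lets the active-versus-sham difference vary with the baseline predictor. Comparing theta between arms shows whether stimulation changes theta. A covariate main effect shows who improves whichever arm they are in, and the cognitive training is offered in both arms. Neither shows who benefits from active stimulation.

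An analyst who followed sections 11 and 14 as written would produce no estimate for two predictors that the aims name. The choice of theta measure, visit, outcome and sample would then be made after the data are seen, or that part of the aims would go unreported.

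**Working it through.** The plan gives no power or precision figure for any predictor analysis, so there is none to reproduce. The main check is a comparison of the texts.

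**Step 1. Predictors by place in the document.**

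| Predictor | S.1, Aim 1.3 | S.1, Aim 2.3 | S.10, Aim 1.3 | S.10, Aim 2.3 | Models, S.11 and S.14 |
|---|---|---|---|---|---|
| EEG frontal theta synchrony | yes | yes | no | no | no |
| Neuroimaging abnormality | yes | yes | yes | yes | no |
| Injury severity | yes | yes | yes | yes | yes |
| Premorbid intelligence (WTAR) | yes | yes | yes | yes | yes |
| Symptom burden | yes | yes | NSI | BDI and HAM-D | NSI |

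Five predictors are named for Aim 1.3 and three reach the models, so 5 − 3 = 2 have no term. The dependent variables in sections 11 and 14 are the EXAMINER composites, the NSI cognitive score and PROMIS-29. BDI-II and HAM-D are not among them, so no model is written for Aim 2.3.

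**Step 2. The term that would be needed.** For a post-stimulation outcome, write: mean = b0 + b1·arm + b2·predictor + b3·(arm × predictor) + baseline outcome. Only b3 addresses moderation. Entering a predictor as a covariate gives b2. No b3 is written explicitly for any predictor.

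**Step 3. Precision for theta.** Assumptions (not in the documents): two-sided 0.05, 80% power, equal arms, residual SD 1, and baseline theta standardised to SD 1. With n/2 participants per arm, each arm's slope has variance 2/n. The difference in slopes therefore has variance 4/n and standard error 2/√n. The detectable difference is (1.960 + 0.842) × 2/√n:

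- n = 80 (all TBI participants): 5.604/8.944 = 0.63
- n = 60: 5.604/7.746 = 0.72
- n = 40: 5.604/6.325 = 0.89
- n = 30: 5.604/5.477 = 1.02

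These are in residual SDs of outcome per SD of theta. If the sham slope were zero, a slope s would correspond to an active-arm correlation of s/√(1 + s²). That is 0.63/√1.397 = 0.53 at n = 80 and 1.02/√2.040 = 0.71 at n = 30.

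**Step 4. Precision for a yes/no predictor such as MRI abnormality.** With an even split there are four cells of n/4, and the interaction has standard error √(16/n) = 4/√n. The detectable interaction is 2.802 × 4/√n, which is 1.25 SD at n = 80 and 2.05 SD at n = 30. Section 10 plans 30 subjects with MRI. Treating all of them as TBI participants with an even split is favourable to the plan.

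**Step 5. Number of tests.** Three EXAMINER composites plus BDI-II and HAM-D give 3 + 2 = 5 per predictor.

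**The case against.** *The plan does provide for EEG.* Aim 1.3 itself commits to mixed models for a list that includes theta, section 2 intends a correlation with response, and section 11 closes with a general allowance for linear models, machine learning and other methods on EEG data. A reader might infer from the mismatch that the trial cannot test theta as a predictor. The documents do not support that: pre-stimulation EEG may be obtained, and a model could be fitted. What stands is narrower. None of these statements names an outcome, visit, sample or contrast, and the model that is offered for Aim 1.3 contains no EEG term.

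*EEG may be meant as a response marker.* Hypothesis 5 and section 5 treat theta as something that changes, hypothesis 4 omits it, and the Aim 2.3 list is worded as examples. This stands. The text does not settle the role of EEG, and deleting it from the two aims would also reconcile the document.

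*EEG is not a special case.* This also stands. Neuroimaging abnormality has the same gap in the models, and no predictor has a written interaction. The unspecified contrasts leave room for interactions but do not commit to them.

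*The section 2 correlation.* A reader might infer that it would be run in treated patients only, and so could not separate benefit from tDCS from general improvement. Section 2 sets no such restriction. The fair criticism is that it specifies no model, visit or sample.

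**Conclusion.** The inconsistency is real. Theta synchrony is named in both aims and is missing from both section 10 lists and from the models. Neuroimaging abnormality is in both aims and both lists and is missing from the models. The models presented as answering Aim 1.3 therefore cover three of its five predictors, without an explicit interaction for any, and Aim 2.3 has no model.

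This is a gap in specification, and added models would give only wide intervals. For theta, 80% power needs slope differences of about 0.63 to 1.02 residual SD per SD across 80 down to 30 participants with EEG, under the assumptions in the working. The text comparison does not depend on those assumptions.

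A reader might go further and infer that the main efficacy result is compromised. It is not: the primary endpoint and the active-versus-sham comparison do not rely on these predictors. The point is minor to moderate.

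**What to change.** 1. Use one predictor list in section 1 (Aims 1.3 and 2.3), section 10 (Aims 1.3 and 2.3), section 11 and section 14. Settle whether symptom burden in Aim 2.3 means NSI or baseline BDI-II and HAM-D.
2. Decide the role of EEG. If it is not intended as a baseline predictor, remove it from Aims 1.3 and 2.3 and keep it as an outcome; the EEG models below then fall away.
3. Keep the main active-versus-sham model as it is, so that participants without EEG or MRI are not dropped from it.
4. Add separate exploratory models in TBI participants who have the relevant baseline measure. Each contains arm, visit, baseline outcome, the predictor (pre-stimulation frontal midline theta synchrony; likewise MRI abnormality) and its arm-by-predictor term at the post-stimulation visit. The outcomes are the three EXAMINER composites for Aim 1.3, and BDI-II and HAM-D for Aim 2.3.
5. Define the theta measure in advance and state how many TBI participants are expected to have EEG.
6. Report the interaction estimates with confidence intervals, labelled exploratory, and say that they will be imprecise.

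The cost is protocol wording and some extra modelling on measurements already provided for, with no new procedures. The downside is about five extra exploratory tests per predictor (ten if both EEG and MRI are kept), all with wide intervals.
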